## [v] Sample Size

We will recruit a total of up to 1000 neonates at risk for jaundice based on clinical signs and symptoms.

During our pilot study, we evaluated 100 participants and collected 147 samples total. However only 7 samples collected were over 20 mg/dL. In addition to confirming the accuracy of BiliSpec in this validation study, we also want to ensure we have enough samples of clinically high bilirubin concentrations (>20mg/dL) to ensure our device functions properly over our intended dynamic range (0-35 mg/dL). To accomplish this, we will collect data from up to 500 participants at each location. Previous data have determined that the standard deviation of the difference between the Bilirubinometer and our device is 1.0 mg/dL. In order to detect a statistical difference between the Bilirubinometer and our device of 0.8 mg/dL, our target accuracy, at a statistical power of 90% and  $\alpha$  of 0.05 using a paired test, we need 34 samples (8). Since only 7 samples out of 100 participants during our pilot study were over 20 mg/dL, we will need up to 500

participants at each location to acquire the statistically significant number of samples over 20 mg/dL. The larger sample sizes will also us to conclusively validate the accuracy of the BiliSpec system over the full dynamic range of clinically relevant bilirubin concentrations.

In summary, 300 samples at each location are needed to show that the accuracy of BiliSpec is within 0.2 mg/dL of the laboratory standard spectrophotometric measurement (95% power, assuming 0.98 standard deviation of difference based on the pilot study); we have increased the number to up to 500 patients per location (1000 total) to increase the chances of recruiting patients over the full clinically encountered range of bilirubin concentrations, particularly at high concentrations.

This study will enroll up to 500 neonates at Queen Elizabeth Central Hospital and 500 neonates at Kamuzu Central Hospital who are deemed to be at risk for jaundice or who are receiving blue light phototherapy treatment for jaundice. We will compare the detection of bilirubin levels by BiliSpec to bilirubin monitoring with laboratory spectrophotometric bilirubinometry and transcutaneous bilirubinometry, the standard of care in developed settings.

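### The 34 samples given for a paired test do not follow from the stated inputs, which need 19 pairs; 34 is the stated numerical basis for 500 participants per site.

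*Combined protocol and SAP*

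**What the plan says.** Section H.[v] (Sample Size) contains two calculations.

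The first concerns samples above 20 mg/dL. It states that "the standard deviation of the difference between the Bilirubinometer and our device is 1.0 mg/dL", and that the aim is to "detect a statistical difference between the Bilirubinometer and our device of 0.8 mg/dL, our target accuracy", with 90% power and alpha 0.05. Its result is "using a paired test, we need 34 samples (8"). No formula is given, and the text does not say whether the test is one- or two-sided. The section then turns this number into an enrolment figure. It begins "Since only 7 samples out of 100 participants during our pilot study were over 20 mg/dL" and concludes that 500 are needed as "participants at each location to acquire the statistically significant number of samples over 20 mg/dL".

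The second concerns overall accuracy: "300 samples at each location are needed to show that the accuracy of BiliSpec is within 0.2 mg/dL" of the laboratory method, with 95% power and an SD of 0.98. The summary paragraph raises this to 500 patients per site "to increase the chances of recruiting patients over the full clinically encountered range of bilirubin concentrations, particularly at high concentrations". That last reason makes no use of the 34.

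**The concern.** Every input needed for the first calculation except sidedness is stated, so it can be checked directly. For a paired design with a standardised difference of 0.8/1.0 = 0.8, a requirement of 34 pairs looks roughly twice too large.

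The 34 is also the only number in the section that, combined with the pilot yield, gives something close to 500 per site. If it is wrong, the numerical argument for going from 300 to 500 per site fails. That step is up to 200 more neonates at each hospital, or 400 in all, each having a heel stick. An ethics committee reading the section would take 500 as a calculated need, when the stated inputs do not produce it.

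**Working it through.** **Inputs, all from section H.[v].** SD of the paired difference 1.0 mg/dL (0.98 in the second calculation); difference 0.8 mg/dL; power 90%; alpha 0.05; paired test; pilot yield 7 samples above 20 mg/dL from 100 participants (147 samples). Sidedness is not stated. I take two-sided and also show one-sided.

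**Attempt to reproduce 34 as a paired test.**

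- Normal approximation: n = [(z₀.₉₇₅ + z₀.₉₀) × SD/δ]² = (1.960 + 1.282)² × (1.0/0.8)² = 10.507/0.64 = 16.4, so 17 pairs.
- Exact paired t-test (noncentral t, n − 1 degrees of freedom, noncentrality √n × 0.8/1.0): 18 pairs give 89.2% power and 19 give 90.9%. The answer is **19**.
- With SD 0.98: 17 pairs give 88.5% and 18 give 90.4%, so 18.
- At 34 pairs with SD 1.0 the power is 99.5%.

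**Other readings of the paired calculation.**

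| Variant (SD 1.0, difference 0.8) | Pairs |
|---|---|
| One-sided alpha 0.05, 90% power | 15 |
| Two-sided, 95% power | 23 |
| Two-sided, 90% power, Wilcoxon efficiency adjustment | 20 to 22 |
| Equivalence test, margin 0.8, 90% power, one-sided 0.05 or 0.025 (normal approximation) | 17 or 21 |

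None gives 34. Doubling the 17 of the normal approximation, to count two measurements per pair, does give 34. That reading does not fit, because the section applies the number to samples above 20 mg/dL and each such sample supplies one pair.

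**Unpaired calculation.** Treating 1.0 as the SD within each of two independent groups, n per group = 2 × 10.507/0.64 = 32.8, so 33. The exact two-sample t-test gives 89.3% at 33 and 90.2% at 34. So 34 is the unpaired per-group size, although the text does not show that this is how it arose.

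**Comparison with the section's other figure.** For 0.2 mg/dL, SD 0.98 and 95% power, with two-sided alpha 0.05 (not restated there): (1.960 + 1.645)² × (0.98/0.2)² = 12.995 × 24.01 = 312. The exact paired t-test needs 314, and 300 pairs give 94.1%. The unpaired version needs 625 per group, and 300 per group would give 70.4%. The 300 is therefore close to a paired result, and the two figures in the section do not appear to come from the same method.

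**Effect on participants per site.** At 7 high samples per 100 participants:

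- 34/0.07 = 485.7, so 486, which matches the stated 500.
- 19/0.07 = 271.4, so 272.

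These are expected-yield figures. Binomial chances of reaching the target, assuming at most one high sample per participant and the pilot yield at each site:

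| Participants per site | Expected high samples | Chance of at least 19 | Chance of at least 34 |
|---|---|---|---|
| 272 | 19 | 54% | – |
| 300 | 21 | 71% | – |
| 500 | 35 | over 99% | 59% |

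**The case against.** The arithmetic is hard to dispute, so the case for the plan concerns the consequence.

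- **272 is not a safe target.** At 272 participants the chance of obtaining 19 high samples is only 54%. At the same yield, 90% assurance needs 351 participants and 95% needs 377. This stands: 272 is what the protocol's own style of reasoning gives, not a recommended size. By the same standard, 500 gives only a 59% chance of reaching 34.
- **The yield is uncertain.** Seven in 100 has an exact 95% interval of about 2.9% to 13.9%, counting each high sample as a separate participant. At the lower limit 19 high samples need about 664 participants, and 500 would yield about 14. This stands as a reason to keep a generous ceiling, but the section does not make that argument.
- **The unit is unsettled.** The Study Period table (H.[iv]) counts 500 samples per site, and H.[v] moves between samples and patients. Per sample the pilot yield is 7/147 = 4.8%, so 19 high samples need 399 samples on average, and 500 samples give an 87% chance of at least 19. On that reading a corrected 19 would support a ceiling near 500. But the sentence at issue argues from participants to participants, and on the per-sample reading the stated 34 would need 34/(7/147) = 714 samples, so 34 and 500 would not agree.
- **Little harm follows.** The error overpowers the stated comparison, 500 is a ceiling, and extra samples at high concentrations serve the aim of covering 0 to 35 mg/dL. All of this is true and limits the weight of the point. It does not make 34 the right answer to the calculation as described.

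**Conclusion.** The concern holds. On the stated inputs a two-sided paired t-test needs 19 pairs, not 34, and the conclusion is the same for a one-sided test and for the SD of 0.98. The stated number gives 99.5% power where 90% is claimed.

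The derivation of 500 participants per site from that number therefore fails as written. The same reasoning with 19 leads to about 272, below the 300 the section already asks for. That comparison takes the pilot yield at face value and reads the 300 samples as participants, as the summary sentence does when it raises the number to 500 patients.

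The error is conservative and does not threaten the validity of the results. The basis for 300 per site is unaffected, and the separate reason for 500, coverage of the full concentration range, remains available.

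**What to change.** In section H.[v], replace the 34 with 19 and name the test, for example: *with a two-sided paired t-test, 19 paired samples are needed*. Alternatively, show the method and inputs that give 34. Sidedness and test type should be stated in either case, since the current text leaves sidedness open.

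Then rewrite the following sentence so that 500 rests on the coverage reason, for example: *Enrolment of up to 500 per hospital is intended to cover the whole range of concentrations met in practice, high values above all; at the pilot yield of 7 per 100 participants this would give about 35 samples above 20 mg/dL per hospital.* Adding that the yield comes from only seven pilot samples would be fair to the reader.

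If the sponsor prefers to keep 34 as a margin, it should say that this is its own choice and give the SD it assumes; 34 pairs keep 90% power for 0.8 mg/dL up to an SD of about 1.4 mg/dL.

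The cost is two sentences of protocol wording. The ceiling of 500, the 300-per-site basis, the procedures and the analysis need not change.

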In response to this need for early bilirubin monitoring, researchers at Rice University created BiliSpec, a low-cost battery-powered reader designed to immediately quantify serum bilirubin levels from a small drop of whole blood applied to a lateral flow strip. BiliSpec has two components: (1) an inexpensive, disposable lateral-flow strip on which the clinician spots a drop of whole blood from a heel prick and (2) a battery powered reader which measures the light transmitted through the serum on the detection strip and displays a digital report of the bilirubin concentration (Figure 1).

BiliSpec has been evaluated in the laboratory and in a small pilot study (Appendix 3) at QECH to test efficacy and usability (4). The BiliSpec lateral flow strip is capable of handling a range of blood volume to account for variations in volume from heel sticks. Full separation of plasma on the lateral flow strip takes approximately 1-2 minutes. In this time, the lateral flow device is sealed by the user after application of blood to prevent contamination or leaking. Measurement of bilirubin using BiliSpec during the pilot study yielded an average absolute difference of 0.8 mg/dL (95% CI of -1.7-2.2 mg/dL) as compared to the laboratory spectrophotometric measurement. The lateral flow strip costs less than \$0.05 and we estimate the reader can be built for less \$200 at low volume. We are optimizing BiliSpec to achieve a target accuracy of ±20% or 0.4mg/dL, whichever is greater (United States CLIA Standard) with a dynamic range up to 35 mg/dL, consistent with performance of bilirubin measurement techniques used in high-resource settings (3). During the pilot study, 95% of samples were within CLIA guidelines, and simple changes are expected to improve performance. One limitation of the pilot study was the limited range of bilirubin concentrations tested; during the validation study, we will increase the number of neonates tested to increase the number of samples at high bilirubin concentrations. We believe that rapid adoption of this technology is possible since BiliSpec is affordable and simple to use at the bedside.

BiliSpec provides an important tool to monitor the efficacy and progress of phototherapy, ensuring appropriate treatment dosage and duration. Used together, BiliSpec and blue light phototherapy have the potential to reduce the morbidity and mortality associated with neonatal jaundice.

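### The plan promises conclusive validation over the full dynamic range, 0-35 mg/dL, but secures no readings near the top and plans no analysis by concentration

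*Combined protocol and SAP*

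**What the plan says.** All of the high-range reasoning is in section H [v], Sample Size.

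- The aim is to "ensure our device functions properly over our intended dynamic range (0-35 mg/dL").
- The motive is the pilot: "we evaluated 100 participants and collected 147 samples total", of which "only 7 samples collected were over 20 mg/dL". Section E says the same in general terms: "One limitation of the pilot study was the limited range of bilirubin concentrations tested".
- The provision is 34 samples above 20 mg/dL, the number given for detecting a 0.8 mg/dL difference with 90% power. It is to be reached by enrolling up to 500 neonates per site.
- The promised result is that the larger sample will "conclusively validate the accuracy of the BiliSpec system over the full dynamic range of clinically relevant bilirubin concentrations".

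The next paragraph is milder. It gives the larger enrolment only as a way to make coverage of the range more likely.

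Section H [vii], Data Analysis, says that the measurements will be compared. It names no agreement statistic, no breakdown by concentration, and no handling of repeat samples from one neonate.

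**The concern.** The plan can meet its own high-range requirement without learning anything about the top of its range. All 34 samples could lie between 20 and 22 mg/dL. No sub-band, minimum count, quota or enrichment applies between 20 and 35, and enrolment may stop short of its ceiling.

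The analysis would not expose the gap either. If results are pooled, the many low and mid-range pairs dominate the summary, and a device that reads wrongly at 30-35 mg/dL could still show a small average difference. A report following the plan could then state that accuracy was validated to 35 mg/dL with little or no evidence there.

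**Working it through.** **1. The plan's 34.** Inputs from Sample Size: difference 0.8 mg/dL, SD 1.0 mg/dL, power 90%, alpha 0.05, paired test.

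- Paired, two-sided: ((1.960 + 1.282) × 1.0/0.8)² = 16.4, so 17; with the t distribution, 19.
- Two independent groups: 2 × 16.4 = 32.8, so 33 per group; with the t distribution, 34.

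The stated paired test does not give 34; an unpaired calculation does. The error is on the safe side, but 34 has no special standing as a minimum.

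**2. Readings above 20 mg/dL.** The pilot rate is 7/147 = 4.8% of samples (exact 95% interval 1.9% to 9.6%). Sample Size counts participants, with 147/100 = 1.47 samples each in the pilot, so 1000 neonates give 1470 samples. The Study Period table instead plans up to 500 samples per site, 1000 in total.

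- 1470 × 7/147 = 70 readings (35 per site).
- 1000 × 7/147 = 48 readings (24 per site).
- Binomial chance of at least 34 over both sites: above 98% either way. At one site: 59% with 735 samples, 2.5% with 500.

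So at the pilot rate and full enrolment, the band above 20 is likely to be filled over both sites.

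**3. Readings above 30 mg/dL.** This needs an assumption, because no distribution above 20 is given. Take a lognormal with median m and share p above 20:

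- σ = ln(20/m) / z, where z is the upper-p normal quantile (1.668 for p = 7/147)
- expected count = N × [1 − Φ(ln(30/m)/σ)]

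Example, m = 6: σ = 1.204/1.668 = 0.722; ln(5)/0.722 = 2.230; upper tail 0.01287; × 1470 = 18.9.

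Expected readings above 30 over both sites, for N = 1000 to 1470:

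| Share above 20 | m = 6 | m = 8 | m = 10 | m = 12 |
|---|---|---|---|---|
| 1.9% (lower limit) | 2.9-4.2 | 1.4-2.1 | 0.5-0.8 | 0.1-0.2 |
| 4.8% (pilot) | 12.9-18.9 | 8.0-11.8 | 4.1-6.0 | 1.4-2.0 |
| 9.6% (upper limit) | 40.3-59.3 | 29.7-43.7 | 19.2-28.2 | 9.5-14.0 |

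At the pilot rate, a normal tail (mean 8 to 12) gives 0.1 to 1.6, and an exponential tail gives 10 to 15.

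**4. What small counts could show.** This uses the plan's SD of 1.0, treats readings as independent, and assumes that the SD holds at the top.

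- 5 readings: 95% half-width for bias 2.776 × 1.0/√5 = 1.24 mg/dL, wider than the 0.8 target. No failures in 5 still allows a true failure rate up to 1 − 0.05^(1/5) = 45% (one-sided 95%).
- 15 readings: 2.145/√15 = 0.55 mg/dL, and 1 − 0.05^(1/15) = 18%.

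**5. Illustration of masking (hypothetical).** Let 6 of 70 readings above 20 lie at 30-35 mg/dL, each reading 8 mg/dL low. That is outside the ±20% limit in section E, which is 6 to 7 mg/dL at those values. Let all other readings be unbiased.

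- Mean bias above 20: −48/70 = −0.69 mg/dL, inside 0.8.
- Mean bias over all 1470 samples: −48/1470 = −0.03 mg/dL, inside the 0.2 mg/dL in Sample Size.

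A test against zero within the 70 might still flag a difference, but it would not show where the error lies.

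**The case against.** The strongest reply is that the shortage near the top is assumed, not shown. That is right. The spread of the seven high pilot readings is not in the text available, and Appendix 3, to which the pilot results are referred, is not part of it. The medians of 6 to 12 and the lognormal shape come from no section. A reader might infer that the high readings must cluster just above 20, or that very few will fall near 35. The table does not bear that out: at the pilot rate with median 6, 18.9 of 70 (27%) exceed 30, and at the upper limit of the pilot rate with median 6 or 8 the count can pass 34. The pilot was also run at one of the two hospitals only.

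A second reply is that the sentence is sample-size rationale, not an endpoint or decision rule, and that it speaks of clinically relevant concentrations. Both are true. A reader might also infer that the plan takes 34 samples as proof of function to 35 mg/dL. It does not say so: 34 is the number for detecting a 0.8 mg/dL difference. But the same section defines the range as 0-35, and no other rule in the plan limits what may be concluded.

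A third reply is that nothing in the text suggests the device fails at high values. That also stands. The point concerns what the study could show, not a known fault.

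**Conclusion.** The concern holds as a gap between claim and design. The plan states a conclusive result over 0-35 mg/dL, provides for one open band above 20, sets no count near the top, and names no analysis that would show how agreement changes with concentration. These facts come straight from the text and need no model.

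The size is uncertain. The expected number of readings above 30 is about 1 to 19 over both sites at the pilot rate, and about 0.1 to 59 once the pilot interval is included. Both ranges rest on the assumed lognormal with median 6 to 12 and on 1000 to 1470 samples, with full enrolment. The supportable conclusion is that validation near 35 mg/dL is not assured. That it will fail, or that readings there will be too few, cannot be concluded from the documents.

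**What to change.** **Sample Size.** Replace the claim of conclusive validation over the full range with: validate accuracy over the range of concentrations observed. This agrees with the milder paragraph that follows it.

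**Data Analysis.** Prespecify:

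- a plot and a regression of the BiliSpec-minus-bilirubinometer difference on concentration, allowing for repeat samples from one neonate;
- count, bias with 95% CI, limits of agreement, and the share within the plan's own limit (±20% or 0.4 mg/dL, whichever is greater), overall and in descriptive bands that include above 20 mg/dL and sub-bands above it;
- a statement that the validated range will be limited to concentrations where the data support it, with sparse results above that labelled descriptive.

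Do not make 34 samples per band the test of the validated limit. The figure does not follow from the stated paired test. The rule could also set the limit at 20 mg/dL despite about 48 readings above it: with 1000 samples, the chance of 34 readings between 20 and 25 is only 2% to 18% at medians 6 to 8.

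**Cost.** Wording, one plot, one regression and simple tables on data already being collected; no extra neonates or blood. The real price is that the validated range reported may be narrower than 0-35 mg/dL.

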## [vi] Data Collection

## **Training**

- 1. Prior to the start of the study, all study nurses/clinicians will receive training from a trained study engineer on BiliSpec and transcutaneous bilirubinometer use. Each member will pass a standard evaluation in order to operate the devices.
- 2. The local researchers will be available on site or by phone, email, and site visits to respond to any questions and/or concerns. The US based researchers will be in frequent contact with the local team.

#### Informed Consent

The investigator will provide details of the study to the guardians of all eligible subjects and will answer any questions. Guardians who consent to participation will be asked to sign a form documenting their consent (Consent Forms in Appendix 1) prior to the start of any study procedures.

Documentation of the consent process includes the following elements:

- Date of consent;
- Topics discussed with the subject's guardian (e.g. risk, benefits, etc.); and
- Confirmation that the consent was reviewed, that the guardian's questions were answered, and that a signed copy of the consent was provided to the subject's guardian.

The consent form will be updated or revised whenever important new safety information is available, whenever the protocol is amended, or whenever any new information becomes available that may affect participation in the study.

## **Enrollment**

Enrollment will be after fully informed and written consent from the parent or guardian. Guardians will not be required in any way to have their child participate. If they choose not to participate, the care of their child will not be jeopardized. A parent will be free to withdraw their child from participating at any time, without explanation and such a decision will not affect standard of care. Each participant will be compensated 10USD (in local currency) per visit.

A participant identification number will be assigned. This number will be used for identification purposes throughout the study.

# **Bilirubin Testing of Neonates**

The trained study nurse will assess the subject for clinical complications before performing the necessary heel prick blood draw.

- A transcutaneous measurement of bilirubin and a heel stick will be performed on the neonate by a trained study nurse or clinician.
- One drop of blood will be collected on the sample card and immediately used for analysis. BiliSpec will be operated by a trained nurse or trained research assistant.
- Another drop of blood, collected in a capillary tube, will be centrifuged and then measured using the laboratory spectrophotometric bilirubinometer (Reichert UNISTAT®
  Bilirubinometer 1310310C). The spectrophotometric bilirubinometer will be operated by trained research assistants from the Rice department of bioengineering and the University of Malawi. Bilirubin concentration values measured by the gold standard laboratory bilirubinometer will be used to guide diagnosis.

Measurements will be made at multiple time points as indicated clinically.

Data will be collected on paper forms (Appendix 2) as is consistent with current clinical practice. Clinical and/or research personnel will record information, excluding personal identifiers, on a standardized patient monitoring form. After the patient's participation is completed, a research assistant will collect and scan the form.

The following section details the variables that will be measured or calculated in the pilot study.

